	Grade 3 and 4	
Permanently discontinue patient from study treatment.
 
Toxicity Management:
 
 • Hospitalization required. • Promptly initiate empiric high-dose methylprednisolone IV treatment (e.g., 500-1000 mg/day for 3 days), followed by at least 1.0 mg/kg/day of prednisone (or equivalent) for a minimum of 14 days or until complete resolution of clinical symptoms and chest CT findings, followed by gradual taper over at least 4 weeks. • Re-image as clinically indicated. • If still no improvement within 3 to 5 days, 
 – Re-consider additional work-up for alternative etiologies as described above. – Consider other immunosuppressants and/or treat per local practice.

CONFIDENTIAL

	Worst Toxicity NCI CTCAE Version 5.0 Grade (unless otherwise specified)	Schedule Modification for Patritumab deruxtecan
Eye disorders		
Ocular	Grade 3	Delay dose until resolved to \leq Grade 2, then: 
 If resolved in ≤ 7 days, resume patritumab deruxtecan. If resolved in > 7 days, then reduce patritumab deruxtecan by 1 dose level. Ophthalmologist consultation as necessary.
	Grade 4	Discontinue patient from patritumab deruxtecan. Ophthalmologist consultation as necessary.
Renal and urinary disorders		
Creatinine increased	Grade 3 ($> 3.0 \times$ baseline; $> 3.0-6.0 \times$ ULN)	Delay dose until resolved to \leq Grade 1 or baseline, then reduce patritumab deruxtecan by 1 dose level.
	Grade 4 ($> 6.0 \times$ ULN)	Discontinue patient from patritumab deruxtecan.
Hepatobiliary disorders		
AST or ALT increased without TBL increased	Grade 2 ($> 3.0-5.0 \times$ ULN if baseline was normal; $> 3.0-5.0 \times$ baseline if baseline was abnormal)	Continue patritumab deruxtecan. In patients without liver metastasis, monitor AST/ALT 24 to 72 hours later, and continue regular monitoring until resolution.
	Grade 3 ($> 5.0-20.0 \times$ ULN if baseline was normal; $> 5.0-20.0 \times$ baseline if baseline was abnormal). In patients without liver metastases and patients with liver metastases and baseline level $\leq 3 \times$ ULN.	Delay patritumab deruxtecan dose until resolved to \leq Grade 1, then: 
 If resolved in ≤ 7 days, resume patritumab deruxtecan. If resolved in > 7 days, then reduce patritumab deruxtecan by 1 dose level.

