	$> 8.0-20.0 \times$ ULN if baseline was normal; $> 8.0-20.0 \times$ baseline if baseline was abnormal. In patients with liver metastases, if the baseline level was $> 3 \times$ ULN.	Delay patritumab deruxtecan dose until resolved to \leq baseline level, then: 
 If resolved in ≤ 7 days, resume patritumab deruxtecan. If resolved in > 7 days, then reduce patritumab deruxtecan by 1 dose level.

CONFIDENTIAL

	Worst Toxicity NCI CTCAE Version 5.0 Grade (unless otherwise specified)	Schedule Modification for Patritumab deruxtecan
	Grade 4 ($>20.0 \times$ ULN if baseline was normal; $>20.0 \times$ baseline if baseline was abnormal)	Discontinue patient from patritumab deruxtecan. Gastroenterologist or hepatologist consultation as necessary.
TBL increased	Grade 2 (>1.5 - $3.0 \times$ ULN if baseline was normal; >1.5 - $3.0 \times$ baseline if baseline was abnormal)	
If no documented Gilbert's syndrome or liver metastases at baseline, delay patritumab deruxtecan dose until resolved to \leq Grade 1, then:
 
 • If resolved in ≤ 7 days, resume patritumab deruxtecan. • If resolved in >7 days, then reduce patritumab deruxtecan by 1 dose level. 
If documented Gilbert's syndrome or liver metastases at baseline, continue patritumab deruxtecan.

	Grade 3 (>3.0 - $10.0 \times$ ULN if baseline was normal; >3.0 - $10.0 \times$ baseline if baseline was abnormal)	
If no documented Gilbert's syndrome or liver metastases at baseline, delay patritumab deruxtecan dose until resolved to \leq Grade 1, then:
 
 • If resolved in ≤ 7 days, then reduce patritumab deruxtecan by 1 dose level. • If resolved in > 7 days, discontinue patritumab deruxtecan. 
If documented Gilbert's syndrome or liver metastases at baseline, delay patritumab deruxtecan dose until resolved to \leq Grade 2, then:
 
 • If resolved in ≤ 7 days, then reduce patritumab deruxtecan by 1 dose level. • If resolved in >7 days, discontinue patritumab deruxtecan.
	Grade 4 ($>10.0 \times$ ULN if baseline was normal; $>10.0 \times$ baseline if baseline was abnormal)	Discontinue patient from patritumab deruxtecan.

CONFIDENTIAL

	Worst Toxicity NCI CTCAE Version 5.0 Grade (unless otherwise specified)	Schedule Modification for Patritumab deruxtecan

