AST or ALT increased and TBL increased	AST or ALT $\geq 3 \times$ ULN with simultaneous TBL $> 2 \times$ ULN	
Delay patritumab deruxtecan until drug-induced liver injury can be ruled out. The Investigator should consult with a gastroenterologist or hepatologist as needed, and the patient should be treated accordingly.
 
Monitor AST/ALT and TBL twice weekly until resolution or return to baseline.
 
It is strongly recommended to perform a full diagnostic workup, to exclude alternative causes such as viral or autoimmune hepatitis, alcoholic liver injury, biliary tract disorders, or hemodynamic abnormalities. Results from diagnostic workup (including, for example: INR, direct bilirubin, serologic tests for hepatitis A, B, and C; alcohol use, ultrasound, MRI, CT scan, concomitant medication use, immunoglobulin levels, ECHO) should be recorded within the eCRF.
 
If drug-induced liver injury is ruled out, the patient should be treated accordingly, and resumption of patritumab deruxtecan may occur after discussion between the Investigator and Sponsor.
 
Patritumab deruxtecan will be permanently discontinued if drug induced liver injury cannot be ruled out from diagnostic workup.

AST or ALT $> 3.0 \times$ ULN (if liver metastases are present, $> 5 \times$ULN) with known hepatitis B and/or hepatitis C infection at baseline	--	
Delay patritumab deruxtecan until reactivation of Hepatitis B and/or Hepatitis C can be ruled out. Perform HBV DNA and/or HCV RNA to rule out reactivation of Hepatitis B and/or Hepatitis C, respectively.
 
Hepatologist and infectious disease consultations are recommended.
 
If reactivation of Hepatitis B and/or Hepatitis C is confirmed, permanently discontinue patritumab deruxtecan.

CONFIDENTIAL

	Worst Toxicity NCI CTCAE Version 5.0 Grade (unless otherwise specified)	Schedule Modification for Patritumab deruxtecan
Gastrointestinal disorders		
Nausea	Grade 3 (Inadequate oral caloric or fluid intake; tube feeding, total parenteral nutrition [TPN], or hospitalization indicated)	Delay patritumab deruxtecan until resolved \leq Grade 1, and consider treatment with antiemetics and/or corticosteroids as per Investigator's judgement and local practice/guidelines, then: 
 • If resolved to \leq Grade 1 in ≤ 14 days, resume patritumab deruxtecan. • If resolved to \leq Grade 1 in > 14 days, then reduce patritumab deruxtecan by 1 dose level.

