Vomiting	Grade 3 (Tube feeding, TPN, or hospitalization indicated)	Delay patritumab deruxtecan until resolved \leq Grade 1, and consider treatment with antiemetics and / or corticosteroids as per Investigator's judgement and local practice/guidelines, then: 
 • If resolved to \leq Grade 1 in ≤ 7 days, resume patritumab deruxtecan. • If resolved to \leq Grade 1 in > 7 days, then reduce patritumab deruxtecan by 1 dose level.
	Grade ≥ 4	Discontinue patient from patritumab deruxtecan.
Premedicate with a two or three drug combination regimen (e.g., dexamethasone with either a 5-HT3 receptor antagonist or an NK-1 receptor antagonist as well as other drugs as indicated) for prevention of chemotherapy-induced nausea and vomiting (CINV).		
Diarrhea/Colitis	Grade 3	Delay patritumab deruxtecan until resolved \leq Grade 1, and consider treatment per local practice/guidelines, then: 
 • If resolved to \leq Grade 1 in ≤ 7 days, resume patritumab deruxtecan. • If resolved to \leq Grade 1 in > 7 days, then reduce patritumab deruxtecan by 1 dose level.
	Grade 4 (Life-threatening consequences; urgent intervention indicated)	Discontinue patient from patritumab deruxtecan.
Mucositis oral	Grade 3	Delay patritumab deruxtecan until resolved \leq Grade 1, and consider treatment per local practice/guidelines, then: 
 • If resolved to \leq Grade 1 in ≤ 14 days, resume patritumab deruxtecan. • If resolved to \leq Grade 1 in > 14 days, then reduce patritumab deruxtecan by 1 dose level.

CONFIDENTIAL

	Worst Toxicity NCI CTCAE Version 5.0 Grade (unless otherwise specified)	Schedule Modification for Patritumab deruxtecan
	Grade 4 (Life-threatening consequences; urgent intervention indicated)	Discontinue patient from patritumab deruxtecan.
Other adverse events (Non-laboratory or Laboratory)	Grade 3	Delay patritumab deruxtecan until resolved \leq Grade 1, or baseline, then: 
 • If resolved in ≤ 7 days, resume patritumab deruxtecan. • If resolved to in > 7 days, then reduce patritumab deruxtecan by 1 dose level.
	Grade 4 (Life-threatening consequences; urgent intervention indicated)	Discontinue patient from patritumab deruxtecan.

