6.2.2 Specific Recommendations for Liver Function Test Abnormalities

For patients with Grade 3 liver enzyme elevations (AST/ALT), patritumab deruxtecan should be held until the values recover to \leq Grade 1. Patients with an elevation of ALT/AST $\geq 3 \times$ ULN in conjunction with a bilirubin $\geq 2 \times$ ULN may remain in the study if a correctable, non-drug-related cause of the liver test evaluations can be documented; otherwise, the patient must be discontinued from the study.

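### Table 4's liver rows do not meet: with bilirubin above 1.5 and up to 2 x ULN, Grade 3 AST/ALT can fall only in a row that conflicts with the Section 6.2.2 hold

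*Combined protocol and SAP*

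**What the plan says.** Several parts of the protocol bear on a patient with raised transaminases and raised bilirubin (TBL).

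- **Table 4, AST/ALT rows.** All graded instructions (Grade 2, both Grade 3 variants, Grade 4) stand under "AST or ALT increased without TBL increased". Grade 3 is a delay and Grade 4 a discontinuation. The heading gives no number for TBL.
- **Table 4, TBL row.** It starts at Grade 2, above 1.5 and up to 3.0 x ULN with a normal baseline, or the same multiples of baseline if that was abnormal. Without Gilbert's syndrome or liver metastases the drug is delayed. Otherwise the instruction reads: "syndrome or liver metastases at baseline, continue patritumab deruxtecan".
- **Table 4, combined row.** "AST or ALT increased and TBL increased" applies from AST or ALT 3 x ULN, with simultaneous TBL above 2 x ULN.
- **Table 4, hepatitis row.** A delay at any bilirubin, but only for patients "with known hepatitis B and/or hepatitis C infection at baseline".
- **Table 4, catch-all row.** The last entry, beginning "Other adverse events (Non-laboratory or Laboratory", delays at Grade 3 and discontinues at Grade 4.
- **Section 6.** Toxicity of Grade 3 or higher is withheld to Grade 1 or baseline and then restarted, if appropriate, one dose level lower. The organ system with the worst toxicity governs.
- **Section 6.2.2.** "For patients with Grade 3 liver enzyme elevations (AST/ALT), patritumab deruxtecan should be held until the values recover to" Grade 1 or lower, with no condition on bilirubin or metastases. A second rule covers AST/ALT of at least 3 x ULN with bilirubin of at least 2 x ULN: unless a correctable cause unrelated to the drug is documented, "otherwise, the patient must be discontinued from the study".

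**The concern.** The first heading turns AST/ALT rules off when bilirubin is increased, and the combined row turns them on again only above 2 x ULN. If 'increased' begins where the TBL row begins, there is a band between the two in which AST/ALT has no graded liver row. The row that remains is graded on bilirubin alone and, for patients with baseline liver metastases or Gilbert's syndrome, says to continue. Read by itself, Table 4 then gives a less strict action when a second liver value is also abnormal.

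Patients with liver metastases are eligible, and Section 11.4 makes potential Hy's Law elevations an event of special interest. Sites (about 10 are planned) could hold, continue or stop for the same laboratory values. Dose holds, discontinuations for adverse events and exposure after a liver event, which feed the safety summaries of Section 10.4.3, would then partly reflect which passage was followed. The ORR and PFS-6 calculations and their confidence intervals are not at issue.

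**Working it through.** The plan gives no figure to reproduce here, so the check applies the written conditions to example values. Values are multiples of ULN, both baselines are normal, liver metastases are present at baseline and hepatitis B/C is not known. 'TBL increased' is taken as the TBL row's lowest entry, above 1.5.

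| AST/ALT | TBL | Table 4 liver rows that apply | Section 6.2.2 |
|---|---|---|---|
| 6 or 10 (Grade 3) | 1.2, 1.5 | AST/ALT Grade 3: delay | hold |
| 6 or 10 | 1.6, 1.8 | TBL Grade 2: continue | hold |
| 6 or 10 | 2.0 | TBL Grade 2: continue | hold, and the second rule |
| 6 or 10 | 2.1 | combined row: delay (TBL Grade 2 also applies) | hold, and the second rule |
| 25 (Grade 4) | 1.2, 1.5 | AST/ALT Grade 4: discontinue | neither rule |
| 25 | 1.6, 1.8 | TBL Grade 2: continue | neither rule |
| 25 | 2.0 | TBL Grade 2: continue | second rule |
| 25 | 2.1 | combined row: delay (TBL Grade 2 also applies) | second rule |

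**Grade 3.** In the band, the TBL row's instruction conflicts with the Section 6.2.2 hold, with the Section 6 rule to withhold, and with the catch-all delay.

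**Grade 4.** Below 2.0 neither sentence of Section 6.2.2 applies. The conflict is with Section 6 (withhold, then a lower level) and with the catch-all row (discontinue), and these two also differ from each other.

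**The boundary.** At exactly 2.0 x ULN the second rule of Section 6.2.2 (at least 2) applies, but Table 4's combined row (above 2) does not. Section 11.4.2 also uses above 2.

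**Variants.**
- *No liver metastases or Gilbert's syndrome.* The TBL row delays, so the hold agrees. Its release condition refers to bilirubin only. Once TBL is back to 1.5 or below, the AST/ALT rows apply again under their own heading, which limits the consequence.
- *Known hepatitis B/C.* At AST/ALT 10 and TBL 1.8, the hepatitis row also applies and delays.
- *Abnormal baseline TBL.* From a baseline of 1.6, a value of 1.9 is 1.9/1.6 = 1.19 x baseline. That is not Grade 2, so the AST/ALT Grade 3 row applies. A value up to 2.0 x ULN can be Grade 2 only if baseline is below 2.0/1.5 = 1.33 x ULN.

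**Sensitivity to the undefined term.** If 'increased' means any value above ULN, the band widens to 1.0–2.0 x ULN. If it means above 2 x ULN, the band disappears.

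**Size.** Section 1.1.3 reports AST increase of Grade 3 or higher in 8/144 = 5.6% of patients in the earlier study (exact 95% CI 2.4% to 10.7%). Over 121 patients that is 0.056 x 121 = 6.7 (2.9 to 12.9). The documents do not give the share with TBL in the band. Assuming 10% to 30% would give 0.7 to 2.0 patients, and fewer once restricted to the branch that says continue. These figures show scale only.

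**The case against.** The strongest reply is that the patient is already covered. Section 6 withholds for any toxicity of Grade 3 or higher, with no exception for bilirubin or metastases. If the AST/ALT value falls outside every named row, the catch-all row covers it within Table 4. The TBL instruction concerns bilirubin and does not cancel a separate rule for AST/ALT. This much stands: a reader might infer that the protocol leaves these patients without an instruction, or directs sites to continue through Grade 4 AST/ALT, and the documents support neither. The defect is conflicting text.

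The reply does not settle which text governs. The worst-organ rule does not choose between two liver values. The catch-all is for other events, and AST/ALT has rows of its own. Section 6 restarts at a lower level, whereas Table 4's Grade 3 AST/ALT row resumes without reduction if recovery takes 7 days or less.

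A second reply is that the two headings are a pair, so 'without' is simply the complement of the combined row's cut. That reading is reasonable and closes the gap, but the first heading does not state it, and the TBL row starts lower.

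A reader might also infer that patients admitted under inclusion criterion 13 with bilirubin already raised start outside the AST/ALT rows. That needs a reading against ULN. Table 4 grades against baseline when baseline is abnormal, so they are not Grade 2 at entry.

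**Conclusion.** The point holds as a conflict between passages, conditional on reading 'TBL increased' at the TBL row's Grade 2 cut. It concerns patients without known hepatitis B/C, with normal baseline bilirubin and TBL above 1.5 and up to 2 x ULN. It is sharpest for Grade 3 AST/ALT with liver metastases or Gilbert's syndrome documented at baseline, where continue stands against the Section 6.2.2 hold, Section 6 and the catch-all row.

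It is tempting to say that Section 6.2.2 is contradicted for Grade 4 as well. By its wording that is so only at exactly 2.0 x ULN, through the second rule; below that, the conflict is with Section 6 and the catch-all row. The mismatch between above 2 and at least 2 x ULN does not depend on how 'TBL increased' is read.

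The number of patients affected cannot be derived from the documents and is likely to be very small. The case for acting is that each instance is a hold, continue or stop decision on a liver signal, and the correction costs little.

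**What to change.** Reconcile Table 4, Section 6 and Section 6.2.2 so that each combination of AST/ALT and TBL leads to one instruction. In particular:

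- define 'TBL increased' in the first heading, including whether it is judged against ULN or baseline;
- cover Grade 4 AST/ALT explicitly when the passages are reconciled;
- say whether release under the TBL row also depends on AST/ALT;
- align above 2 with at least 2 x ULN across Table 4, Section 6.2.2 and Section 11.4.2;
- state which passage prevails when two apply.

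The bilirubin cut and the action are for the sponsor's medical team; none is proposed here. The cost is a wording change at the next amendment, with no new tests or patients.

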10. Patients who have received radiation or surgery for brain metastases are eligible if therapy was completed ≥ 4 weeks prior to initiation of study treatment (2 weeks for patients who received palliative radiation therapy), there is no evidence of central nervous system disease progression on a scan or mild neurologic symptoms, and there is no requirement for chronic corticosteroid therapy for the treatment of brain metastases.
11. Willingness to undergo pre-treatment biopsy and on-treatment biopsies. Must have a tumor amenable to pre-treatment biopsy (unless archived tissue is available and was obtained within 2 months prior to starting treatment) and on-treatment biopsy (excludes bone lesions and previously irradiated lesions).
12. Eastern Cooperative Oncology Group (ECOG) Performance Status score of 0 or 1 (Appendix A)

CONFIDENTIAL

13. Has adequate organ function within 7 days before the start of study treatment, defined as:

- Platelet count $\geq 100 \times 10^9/L$
- Hemoglobin (Hb) ≥ 9 g/dL (transfusion and/or growth factor support allowed)
- Absolute neutrophil count $\geq 1.5 \times 10^9/L$
- Prothrombin time (PT) and partial thromboplastin time (PTT) $\leq 1.5 \times$ the upper limit of normal (ULN), except for patients on coumadin-derivative anticoagulants or other similar anticoagulant therapy, who must have PT-international normalized ratio (INR) within therapeutic range as deemed appropriate by the Investigator.
- Serum creatinine $\leq 1.5 \times$ ULN, or creatinine clearance ≥ 50 mL/min as calculated using the modified Cockcroft-Gault equation; confirmation of creatinine clearance is only required when creatinine is $>1.5 \times$ ULN.
- AST/ALT $\leq 3 \times$ ULN (if liver metastases are present, $\leq 5 \times$ ULN)
- Total bilirubin $\leq 1.5 \times$ ULN if no liver metastases or $<3 \times$ ULN in the presence of documented Gilbert's syndrome or liver metastases
- Serum albumin ≥ 2.5 g/dL

14. Male patients with female partners of childbearing potential and female patients of childbearing potential are required to use two forms of acceptable contraception (Appendix C), including one barrier method, during their participation in the study and for at least 7 months following last dose. Male patients must also refrain from donating sperm during their participation in the study.

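### For patients with liver metastases and baseline AST/ALT above 3×ULN, one limb of the Table 4 row can never apply, no AST/ALT-only row acts at >5 to 8×baseline, and the hold and restart rules in Sections 6 and 6.2.2 do not match

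*Combined protocol and SAP*

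**What the plan says.** Four places bear on an isolated AST/ALT rise, that is, one without raised bilirubin.

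- **Table 4, Grade 3 row (Section 6.2).** Grade 3 is >5.0-20.0×ULN from a normal baseline, or >5.0-20.0×baseline from an abnormal one. The hold is restricted: "In patients without liver metastases and patients with liver metastases and baseline level" no higher than 3×ULN.
- **Table 4, next row.** The trigger is >8.0-20.0×"ULN if baseline was normal", or >8.0-20.0×"baseline if baseline was abnormal. In patients with liver metastases, if the baseline level was" above 3×ULN. The instruction is "Delay patritumab deruxtecan dose until resolved to" the baseline level or lower. Dosing then resumes unchanged if recovery took 7 days or less, and one dose level down if it took longer.
- **Section 6.2.2.** "For patients with Grade 3 liver enzyme elevations (AST/ALT), patritumab deruxtecan should be held until the values recover to" Grade 1 or lower. There is no exception for liver metastases or a raised baseline, and no deference to Table 4.
- **Section 6, general rule.** Toxicity of Grade 3 or worse is withheld until Grade 1 or lower, or until the baseline value if baseline was above Grade 1. Dosing then restarts one level down if appropriate.

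Inclusion criterion 13 (Section 3.1.1) allows AST/ALT up to 3×ULN, and up to 5×ULN "if liver metastases are present". Patients with baseline >3 to 5×ULN are therefore eligible, and the second Table 4 row is written for them.

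**The concern.** The row is confined to patients whose baseline exceeds 3×ULN, yet it opens with a trigger for patients whose baseline was normal. Nobody can be both. What is left is a multiple of an already raised baseline, which puts the hold at a very high absolute level. The row above, which would have acted earlier, shuts this group out.

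A site treating such a patient finds no AST/ALT-only instruction in Table 4 between >5 and 8×baseline, but finds a hold in Section 6.2.2 and another in Section 6. It also finds different restart conditions. Whether a patient is dosed, held or restarted could then depend on which page the site opens. That bears on patient safety, and it makes exposure and hepatic safety data harder to interpret across sites. AST and ALT increases are identified risks of the drug (Section 1.2). The definitions of ORR and PFS-6 are not affected.

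**Working it through.** **Inputs.** Row population: liver metastases and baseline B >3×ULN (Table 4). Eligibility ceiling: B ≤5×ULN (criterion 13). Multiples for an abnormal baseline, from Table 4: Grade 2 starts above 3.0×B, Grade 3 above 5.0×B, this row's hold above 8.0×B, and Grade 4 above 20.0×B.

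**Step 1: the normal-baseline limb.** It needs B ≤1×ULN and B >3×ULN together. No value satisfies both, so the limb is empty. It could apply only if the two conditions referred to different enzymes, and the text does not say so.

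**Step 2: the limb that remains.** The table gives only multiples, so convert them: threshold in ×ULN = multiple × B.

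| Baseline B (×ULN) | Grade 1 ceiling, 3×B | Grade 3 starts above, 5×B | This row holds above, 8×B | Grade 4 starts above, 20×B |
|---|---|---|---|---|
| 3 (boundary, not itself in the row) | 9 | 15 | 24 | 60 |
| 4 | 12 | 20 | 32 | 80 |
| 5 | 15 | 25 | 40 | 100 |

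**Step 3: the range without an AST/ALT-only action in Table 4.** The Grade 2 row (continue) stops at 5×B. The Grade 3 hold row excludes the group. This row starts above 8×B. The uncovered range is therefore >5 to 8×B: 15-24×ULN at the baseline-3 boundary, 20-32×ULN at B = 4, and 25-40×ULN at B = 5. There is also a jump at the boundary. A patient with liver metastases and B exactly 3×ULN is held above 5 × 3 = 15×ULN; one just above 3×ULN is held by Table 4 only above about 8 × 3 = 24×ULN.

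**Step 4: the other sections in that range.** Under Table 4's own grading, >5 to 8×B is Grade 3. Section 6.2.2 withholds, and so does Section 6. Example: B = 4×ULN, AST 24×ULN, normal bilirubin. 24 / 4 = 6×B, so both sections hold and no AST/ALT-only row of Table 4 acts.

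**Step 5: restart.**

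| Source | Value to reach | In ×ULN for B = 3 to 5 | Dose on restart |
|---|---|---|---|
| Table 4 row | ≤B | 3 to 5 | Same if recovered in ≤7 days, otherwise one level down |
| Section 6.2.2 | ≤Grade 1, i.e. ≤3×B | 9 to 15 | Not stated |
| Section 6 | ≤Grade 1, or baseline if baseline was >Grade 1 | 9 to 15, or 3 to 5 | One level down |

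Which Section 6 condition applies depends on whether a raised baseline is graded against ULN or against itself. The protocol does not say.

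**The case against.** The strongest reply is that these are not opposing orders. Table 4 says nothing at >5 to 8×baseline, and where it means dosing to go on it says so, as in its Grade 2 row. A site could obey everything by holding at Grade 3 under Sections 6 and 6.2.2 and applying the special row above 8×baseline. The restart conditions can be stacked too: a value at or below baseline is also within Grade 1 on Table 4's scale, so waiting for baseline satisfies Section 6.2.2.

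Much of this stands. A reader might infer that Table 4 directs dosing to continue at 15-40×ULN. The documents do not support that: the table is silent rather than permissive, and 15-40 joins the lower end of one patient's range to the upper end of another's.

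It does not remove the problem. If treatment is always held from 5×baseline, a separate 8×baseline trigger has no function as a hold threshold, so the row looks like an intended exception. Table 4 does depart from the Section 6 general rule elsewhere, for example by allowing the same dose after quick recovery. But Section 6.2.2 is itself the specific liver section and has no carve-out. Using Table 4's catch-all row for other adverse events would bring in a further release rule, Grade 1 or baseline. A site following Section 6.2.2 alone could also restart at up to 3×baseline, which the special row does not allow.

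A reader might also tie this to Hy's law. Those events have their own Table 4 hold (AST/ALT ≥3×ULN with bilirubin >2×ULN) and their own reporting in Section 11.4.2. Neither depends on this row.

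The affected group may be small. The earlier study had Grade 3 or higher AST increase in 8 of 144 patients (5.6%, Section 1.1.3). If that rate applied here, 121 × 8/144 ≈ 7 patients would have one, and this group is an unknown part of them.

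**Conclusion.** The point holds as an internal inconsistency in a safety rule. One limb of the row is empty by logic. The other triggers a hold only above 24×ULN at the baseline-3 boundary, rising to above 40×ULN at baseline 5. Between >5 and 8×baseline, Table 4's AST/ALT-only rows give this group no action, while Sections 6 and 6.2.2 withhold. The restart conditions differ in all three places, and no stated precedence settles it.

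This rests on three assumptions: baseline within the eligibility ceiling of 5×ULN, grading relative to an abnormal baseline as Table 4 defines it, and an isolated AST/ALT rise. The combined-bilirubin rule, and the rule for known hepatitis B or C (>5×ULN with liver metastases), act separately and can hold earlier. The documents do not give the number of patients with baseline above 3×ULN, so the practical frequency is unknown.

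A reader might also infer that >8×ULN was the intended trigger. It would correspond to 8/5 = 1.6 to 8/3 ≈ 2.7×baseline. The documents do not show which trigger was meant, so neither reading can be taken as the sponsor's intention.

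**What to change.** In the next amendment, reconcile four items together: the Table 4 row for liver metastases with baseline above 3×ULN, the Table 4 Grade 3 row above it, the Grade 3 AST/ALT sentence in Section 6.2.2, and the general Grade 3 rule in Section 6. For this group the result should be:

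- one hold trigger that can actually occur;
- a stated action across the whole range, including >5 to 8×baseline;
- one restart condition, covering both the value to reach and the dose level;
- a sentence saying which passage takes precedence.

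The sponsor's medical team decides the threshold and the restart condition; none is proposed here. The cost is wording in two table rows and two short passages, plus notice to sites. No extra tests are needed, because the Schedule of Assessments already has AST and ALT on Day 1 of every cycle.
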